### 3.2 Research Tool

(1) The execution of LTHOT was assessed using a self-designed Long-Term Home Oxygen Therapy Behavior Survey. Given that improper operational skills can affect the effectiveness of long-term home oxygen therapy, the survey primarily includes four dimensions: adherence to home oxygen therapy, cleaning and disinfection, safe oxygen use, and self-monitoring, with a total of 13 items. Each item has two response options: "Yes" and "No," where "Yes" indicates the behavior was performed, and "No" indicates it was not. A score of 1 is awarded for "Yes," and 0 for "No." The higher the total score, the better the patient's long-term home oxygen therapy behavior. The average daily oxygen use time was self-reported by the patient.

(2) LTHOT Health Belief was assessed using the Long-Term Home Oxygen Therapy Health Belief Questionnaire designed by Yan, J. The questionnaire consists of four dimensions and 26 items. Scores are based on the individual's understanding of their ability to engage in long-term home oxygen therapy behaviors. The total score ranges from 0 to 104, with higher scores indicating a higher level of perceived ability to perform long-term home oxygen therapy health behaviors.

(3) Activity of Daily Living (ADL): Daily living ability was assessed using the Activity of Daily Living scale, with a total score range of 14-56 points. A higher score indicates poorer functional ability. A total score greater than 16 points indicates varying degrees of functional impairment, while a score of 22 points or higher indicates significant functional impairment. If the score for any single item exceeds 3 points, or if two or more items score over 3 points, this suggests significant functional impairment.

(4) Ventilation Function Indicators: These include blood oxygen saturation (SpO2), arterial carbon dioxide partial pressure (PaCO2), arterial oxygen partial

---

pressure (PaO2), pH, lung function (FEV1%), dyspnea score, and 6-minute walk distance (6MWD).

(5) Overall cognitive function The Montreal Cognitive Assessment (MoCA) is used to measure overall cognitive function, with a maximum score of 30. The cutoff scores for normal cognitive function are >13 for illiterate individuals, >19 for those with primary education, and >24 for individuals with middle school education or higher.

### **3.3 Data Processing and Statistical Analysis**

1. After the data collection is completed, SPSS 20.0 software is used for statistical analysis.
2. The description of general demographic data and clinical data: Count data are described by frequency and percentage; measurement data are described by median.
3. Comparison of general demographic data and clinical data between the two groups of research subjects: Rank - sum test and X test are used.
4. Comparison of the total scores of long - term home oxygen therapy beliefs at each time point between the two groups of research subjects: Repeated - measures analysis of variance is used.
5. Comparison of the scores of each dimension of long - term home oxygen therapy beliefs, long - term home oxygen therapy behavior scores, and average daily oxygen inhalation time at each time point between the two groups of research subjects: Generalized linear mixed - effect model is used for analysis.
6. Comparison between groups of the total scores and scores of each dimension of long - term home oxygen therapy beliefs, long - term home oxygen therapy behavior scores, and average daily oxygen inhalation time at different time points of the two groups of research subjects: If it conforms to the normal

---

distribution, an independent - sample t - test is used; if it does not conform to the normal distribution, a two - independent - sample rank - sum test is used.

7. Comparison within groups of the total scores and scores of each dimension of long - term home oxygen therapy beliefs, long - term home oxygen therapy behavior scores, and average daily oxygen inhalation time at different time points of the two groups of research subjects: If it conforms to the normal distribution, a paired t - test is used; if it does not conform to the normal distribution, a paired rank - sum test is used.
8. Comparison of the differences in the scores of the Montreal Cognitive Assessment Scale, Mini - Mental State Examination, Geriatric Depression Scale, and Self - rating Anxiety Scale between the intervention group and the control group: An independent - sample t - test is used.

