### **3.1 Object of Study**

1. **Source of the study subjects and the sampling methods:** The study subjects will be selected from the respiratory department of a tertiary hospital in Xiamen, Fujian Province, and a community health service center in Tong'an District, Xiamen. The sampling method is convenience sampling.
2. **Inclusion criteria for the study subjects:**
  - Diagnosed as COPD by a physician.
  - $\text{SpO}_2 < 88\%$  or  $\text{PaO}_2 < 60\text{mmHg}$ .
  - Diagnosed with MCI.
  - Have a home oxygen concentrator.
  - No communication barriers.
3. **Exclusion criteria for the study subject:**
  - Complicated with asthma or lung cancer.
  - Long - term home oxygen therapy time  $\geq 15\text{h/d}$ .
  - Participated in similar interventions.
4. **Samplesize estimation:** The sample size is calculated using the formula for comparing two - sample rates. Referring to the literature, the oxygen therapy compliance rate is 20%, and it is expected to increase by 40% after intervention. With a significance level of 0.05 and a Type II error probability of 0.1, 32 cases are required for each of the intervention group and the control group. Considering a 20% dropout rate, the final sample size is determined to be 39 cases per group, with a total of 78 cases.

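### Baseline data are compared only by significance tests that detect 0.2–0.4 SD imbalances 14–40% of the time, and the outcome comparisons in items 6 and 8 are unadjusted whatever those tests show

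*Combined protocol and SAP*

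**What the plan says.** All references are to the combined protocol and SAP.

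- Section 3.3, item 3: "Comparison of general demographic data and clinical data between the two groups of research subjects" is done by rank-sum and chi-square tests. No significance level is given for these tests, and nothing is said about what follows from their results.
- Section 3.3, item 2: counts are given as frequency and percentage, and "measurement data are described by median". No interquartile range, SD or standardised difference is planned.
- Section 3.3, items 4 to 8: the outcome analyses are repeated-measures ANOVA, a generalized linear mixed model, and t-tests or rank-sum tests. None names a baseline covariate or recruitment site. Item 6 (beliefs, behaviour, daily oxygen time) and item 8 (cognition, depression, anxiety) use two-sample tests, which cannot adjust.
- Section 3.1, item 1: patients come from a tertiary hospital department and a community health centre. "The sampling method is convenience sampling".
- Section 3.1, item 4: "the final sample size is determined to be 39 cases per group, with a total of 78 cases".

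**The concern.** A baseline p-value answers the wrong question in either design. If allocation is random, it tests a null hypothesis already known to be true. If it is not, a non-significant result in groups of this size says little about whether they are alike, because it depends on the sample size as much as on the imbalance. With medians alone, a reader cannot standardise a difference and judge its size.

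The larger matter is what comes after. No adjustment is planned, so an imbalance in a prognostic factor, detected or not, passes into the comparisons in items 6 and 8. Education is an example. Section 3.2 (5) moves the normal MoCA cutoff from above 13 to above 24 according to schooling, so the plan itself treats education as related to the score. Item 8 nevertheless compares MoCA by an unadjusted t-test.

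**Working it through.** **1. The plan's own group size.** The inputs come from section 3.1, item 4. On the rates it states: "the oxygen therapy compliance rate is 20%, and it is expected to increase by 40% after intervention". It also gives an alpha of 0.05, a beta of 0.1 and an allowance of 20% for loss. Take 20% against 60% (absolute increase), two-sided 0.05 and power 0.90. The simple pooled formula is n = 2·p̄(1−p̄)·(z₀.₉₇₅+z₀.₉₀)²/d², with p̄ = 0.40 and d = 0.40:

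2 × 0.40 × 0.60 × (1.960 + 1.282)² / 0.40² = 31.5, so 32.

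This matches "32 cases are required for each of the intervention group and the control group". Then 32 × 1.2 = 38.4, so 39. The sizes used below are 39 at baseline and 39 × 0.8 ≈ 31 analysed.

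**2. What the baseline tests detect at 39 per group.** The two-sided 0.05 level is assumed. For the rank-sum test with normal data, power is approximately Φ(δ·√(n/2)·√(3/π) − 1.96). At δ = 0.4: 0.4 × √19.5 × 0.977 = 1.73, and Φ(−0.23) ≈ 0.41. Simulation (10,000 runs) gives:

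| True imbalance (SD) | Detected | Missed |
|---|---|---|
| 0.2 | 14% | 86% |
| 0.3 | 25% | 75% |
| 0.4 | 40% | 60% |
| 0.5 | 56% | 44% |
| 0.6 | 72% | 28% |
| 0.8 | 92% | 8% |

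Power reaches 50% at δ = 1.96 × √(2/39) × √(π/3) = 0.45 SD. It reaches 80% at 0.643 SD by t-test, slightly higher by rank-sum. For a binary factor, the exact power of the uncorrected chi-square test for 30% against 50% is 44%, so 56% are missed.

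**3. What an imbalance does to an unadjusted comparison.** The documents give neither an imbalance that matters nor a covariate–outcome correlation. Assume a systematic imbalance of 0.4 SD, a correlation ρ and no treatment effect.

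- Shift = 0.4 × ρ. For ρ = 0.5 this is 0.2 SD.
- Noncentrality at 31 per group = 0.2 × √(31/2) = 0.79. The two-sided t-test rejects with probability 12.1%.
- Range: ρ = 0.3 gives a shift of 0.12 SD and 7.5%; ρ = 0.7 gives 0.28 SD and 19%.

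**4. The same, only where the baseline test was non-significant.** The figures in step 3 average over all samples, including the roughly 40% that the baseline test flags. In a simulation with the same inputs (ρ = 0.5, baseline t-test, 60,000 runs), the observed imbalance among non-significant samples averages 0.25 SD. The shift is therefore 0.25 × 0.5 = 0.125 SD, and the false-positive rate is 6.1%.

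**5. If groups are randomised.** There is no systematic imbalance, so the unadjusted test keeps its 5% rate over all allocations. Adjusting for a covariate with ρ = 0.5 would still remove about 0.5² = 25% of the outcome variance.

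**The case against.** Several stronger readings are tempting, and the documents do not support them.

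- *A reader might infer that the tests miss most imbalances that matter.* That holds only below about 0.45 SD, or about 20 percentage points for a binary factor. Larger imbalances are detected more often than missed, and the documents set no threshold for what matters.
- *A reader might infer that a missed 0.4 SD imbalance costs a 12% error rate.* The 12% is the rate over all samples. Where the test actually misses the imbalance, the rate is about 6%.
- *A reader might infer that item 3 is the plan's rule for declaring the groups comparable.* The plan says only that the groups are compared. It attaches no decision to the result.
- *A reader might infer from convenience sampling that the groups are not randomised.* Convenience sampling describes recruitment. The text available to this review does not say how groups are formed, and it cannot be concluded that they are not randomised.
- *A reader might infer that such a bias could account for the expected benefit.* A rise from 20% to 60% is roughly 1.0 to 1.1 SD on a latent scale, so a 0.2 SD shift would not create it.

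It is also fair to say that baseline tests do not themselves bias an outcome result. The repeated-measures analyses in items 4 and 5 may partly absorb a baseline difference in the outcome if baseline is one of the time points, and item 8 might mean change scores. The plan states neither, and neither would deal with imbalance in other covariates.

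What stands is that spread and standardised differences are not planned, and items 6 and 8 use methods that cannot adjust.

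**Conclusion.** The point holds as an inexpensive improvement to the analysis plan. The planned baseline tests are weak for imbalances of 0.2 to 0.4 SD (14% to 40% detected at 39 per group, assuming a two-sided 0.05 level and normal data) and reasonable for large ones. The part that affects results is the absence of prespecified adjustment.

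Its size depends on how the groups are formed. With a systematic 0.4 SD imbalance and a correlation of 0.5, both assumed, the shift is 0.2 SD. The false-positive rate is then about 12% at 31 per group over all samples (7.5% to 19% for correlations of 0.3 to 0.7), and about 6% among samples with a non-significant baseline test. With randomised groups there is no inflation overall, and adjustment gains precision. A 0.2 SD shift could matter more for the item 8 scales, for which no planned effect size is stated.

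**What to change.** **Items 2 and 3.** Report baseline data by group as mean (SD) or median (IQR), or n (%), with standardised differences. Do not use baseline p-values to choose covariates.

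**Items 6 and 8.** Replace the t-test and rank-sum comparisons with regression or ANCOVA, since those tests cannot adjust. Adjust, whatever the observed balance, for a list fixed now: the baseline value of the outcome where measured, recruitment site, age, education level and FEV1%.

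**Item 5.** Add the same covariates to the mixed model.

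Stating how the groups are formed would tell the reader whether adjustment serves mainly to control bias or to gain precision.

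**Cost.** The change uses about five degrees of freedom (six if education enters as the three levels in section 3.2 (5)) with about 62 patients analysed (2 × 31), and it needs slightly more analysis work. FEV1% is already a listed measure; age, education and site are basic data that should be to hand.

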### **3.4 The Project Involves the Implementation Plan of the Ethical Par**

1. **Voluntary Principle:** Ensure informed consent. Before participating in the study, patients are informed of the purpose, content, and procedures of the study. Patients can freely withdraw from the study during the process, and their relevant rights will not be damaged.
2. **Confidentiality Principle:** Seek the opinions of patients on the confidentiality of the research content according to the research questions. Adhere to the confidentiality principle for issues involving participants' privacy and personal safety.
3. **Beneficence and Non - maleficence Principle:** This study has no potential harm to the physical and mental health of patients. On the contrary, the intervention may be beneficial to the implementation of long - term home oxygen therapy and treatment outcomes of patients.

4. **Justice Principle:** Treat all research subjects equally. Whether in the control group or the intervention group, strictly follow the research design plan to conduct the research rigorously and fairly.

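### The belief total is compared between groups without a stated baseline adjustment, and by a method that can rest on fewer patients than the mixed model planned for its own dimensions

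*Combined protocol and SAP*

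**What the plan says.** Section 3.2, item 2, describes the belief instrument: "The questionnaire consists of four dimensions and 26 items", with a total from 0 to 104.

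Three items of Section 3.3 compare its scores between groups:

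- **Item 4**, for the total: "at each time point between the two groups of research subjects: Repeated - measures analysis of variance is used".
- **Item 5**, which opens "Comparison of the scores of each dimension of long - term home oxygen therapy beliefs, long - term home oxygen therapy behavior scores" and also takes in daily oxygen time: "Generalized linear mixed - effect model is used for analysis". It gives no covariates, distribution, random effects or covariance structure.
- **Item 6**, which covers total and dimensions together ("Comparison between groups of the total scores and scores of each dimension of long - term home oxygen therapy beliefs") by t-test or rank-sum test, depending on normality.

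None of the three mentions the baseline score as a covariate, and none is named as the lead result. Section 3.1 expects losses: "Considering a 20% dropout rate, the final sample size is determined to be 39 cases per group, with a total of 78 cases". Section 3.4 adds: "Patients can freely withdraw from the study during the process". No section says how missing scores are handled, and no visit schedule is given.

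**The concern.** Items 4 and 5 ask the same between-group question of one questionnaire and answer it by different methods, with no reason given. Classical repeated-measures ANOVA usually drops any patient with a missed visit, while a likelihood-based mixed model uses every attended visit. A total and the dimensions that make it up could therefore be reported on different patients, and could disagree for that reason alone.

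Item 4 also leaves open which ANOVA effect is the result. The usual tests (group, time, group-by-time) are not a difference at a given visit. Item 6 does give a per-visit difference, but from follow-up scores with no stated use of baseline. With about 31 complete patients per arm, ignoring a correlated baseline score costs real precision.

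**Working it through.** **The plan's own size.** With compliance of 20% against 60% (reading the 40% increase as percentage points), two-sided 0.05 and 90% power:

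n = 2 × 0.40 × 0.60 × (1.960 + 1.282)² / 0.40² = 31.5, so 32 per arm. Then 32 × 1.2 = 38.4, so 39. The stated figures reproduce, and nothing in them depends on beliefs.

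**Patients per method.** Complete patients: 39 × 0.8 = 31.2 per arm, if every dropout misses a visit. Partial data can recover at most 39 × 0.2 = 7.8 per arm, and none if dropouts leave before any follow-up.

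**Assumptions from here on.** The documents give only 39 per arm and 20% dropout. Assumed: three visits (baseline, middle, last), equal correlation ρ between visits, unit SD, arms alike at baseline, and dropout at random unless stated otherwise.

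**Standard error of the last-visit difference, 31.2 complete patients per arm**

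- Unadjusted: √(2/31.2) = 0.253
- Change from baseline: √(2 × 2(1 − ρ)/31.2)
- Baseline-adjusted: √(2(1 − ρ²)/31.2)

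At ρ = 0.6 the last two are √(1.6/31.2) = 0.226 and √(1.28/31.2) = 0.203. Simulation (20,000 trials) agrees and adds the mixed model, which uses all observed follow-up visits, the baseline covariate and an unstructured covariance:

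| ρ | Unadjusted | Change | Adjusted completers | Mixed model |
|---|---|---|---|---|
| 0.4 | 0.254 | 0.279 | 0.235 | 0.233 |
| 0.6 | 0.254 | 0.227 | 0.205 | 0.202 |
| 0.8 | 0.255 | 0.161 | 0.154 | 0.151 |

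At ρ = 0.6, baseline adjustment takes the SE from 0.254 to 0.205; the partial data take it only to 0.202.

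**Power (%) for an assumed 0.5 SD effect at the last visit (10,000 trials)**

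| ρ | Effect at middle, last visit | Group-by-time | t-test | Adjusted completers | Mixed model | Mixed minus group-by-time |
|---|---|---|---|---|---|---|
| 0.4 | 0.5, 0.5 | 43.8 | 49.5 | 55.8 | 55.7 | 11.9 |
| 0.4 | 0.25, 0.5 | 33.8 | 49.8 | 56.2 | 55.9 | 22.1 |
| 0.6 | 0.5, 0.5 | 61.6 | 50.1 | 67.5 | 68.6 | 7.0 |
| 0.6 | 0.25, 0.5 | 48.1 | 49.2 | 67.4 | 68.1 | 20.0 |
| 0.8 | 0.5, 0.5 | 90.1 | 48.4 | 89.8 | 90.4 | 0.3 |
| 0.8 | 0.25, 0.5 | 78.7 | 48.6 | 88.9 | 90.0 | 11.3 |

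If all dropouts leave before any follow-up (ρ = 0.6), group-by-time has 60.8% or 47.4% and the mixed model 67.1% or 66.4%.

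**Bias at the last visit, in SD (ρ = 0.6, no true effect)**

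| Assumed dropout | Unadjusted | Change | Adjusted completers | Mixed model | Group-by-time rejection |
|---|---|---|---|---|---|
| Tied to middle score, one arm | +0.122 | +0.001 | +0.050 | +0.002 | 6.1% |
| Same, both arms | 0.000 | −0.001 | 0.000 | −0.001 | 4.5% |
| Tied to unseen last score, one arm | +0.198 | +0.081 | +0.130 | +0.113 | 6.1% |
| Before any follow-up, tied to baseline, one arm | +0.118 | −0.076 | +0.002 | +0.002 | 6.1% |

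**The case against.** The strongest reply is that nothing here is an error. A total and its subscales may properly have different models. Item 5 groups the dimensions with a yes/no behaviour score and self-reported hours, for which a generalized model is natural, and items 6 and 7 show that distributions were considered. A longitudinal model followed by per-visit tests is also a common layout. This stands, although the plan does not state that reasoning. The missing reason, the unnamed lead test and the absent missing-data sentence are mainly gaps in detail, and they are not peculiar to item 4.

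A reader might infer that complete-case ANOVA biases the belief result and that a mixed model cures it. The documents do not support that. They give no dropout mechanism. The +0.12 SD figure belongs to an unadjusted last-visit comparison with dropout tied to scores in one arm only. In that same case change from baseline is unbiased, and group-by-time rejection stays at 4.5% to 6.1% in all the cases shown. When dropout depends on the unseen score, the mixed model (+0.113) does worse than change from baseline (+0.081).

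Two further limits stand. Item 5 as written names no baseline covariate, so merely moving the total into it would not secure the gain. And the power contrast sets an omnibus test against a test at the visit where the effect was placed; at ρ = 0.8 with a constant effect the advantage disappears. If baseline is one of the ANOVA visits, group-by-time already compares changes, so part of the baseline information is used.

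**Conclusion.** The point holds as a minor, inexpensive improvement. Neither planned between-group analysis of the belief total is stated to adjust for baseline, and the total can rest on different patients from its dimensions: about 31 of 39 per arm under listwise deletion, which is a default and not something the plan states.

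Under the assumed three visits, ρ = 0.6 and 0.5 SD effect, the standard error falls from about 0.25 to 0.20-0.21 SD. Power is about 67-69%, against 50% for the item 6 t-test and 48-62% for group-by-time. Over ρ from 0.4 to 0.8 the gain over group-by-time is about 0 to 22 points. Nearly all of the precision gain comes from the baseline covariate and little from retaining partial data. The text mismatch is certain; every magnitude beyond the 31.2 depends on assumed visits, correlation and effect.

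The stakes are confined to one questionnaire, and the sample size is untouched.

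**What to change.** Replace item 4 with wording such as: *The belief total is analysed by a linear mixed model using all observed follow-up visits, with group, visit, group-by-visit and baseline total as fixed effects and an unstructured within-patient covariance. The reported effect is the group difference with 95% CI at [one follow-up visit named by the sponsor before analysis]. Missing scores are assumed missing at random given the observed scores.*

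Add the same baseline covariate (each score's own baseline) to the item 5 models. Mark the item 6 tests of these scores as supportive. Keep repeated-measures ANOVA, if wanted, as a sensitivity analysis.

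The cost is a few sentences, plus naming the visit, which the sponsor must do because the documents define no schedule. Sample size and software do not change, since a mixed model is already planned. The downside is reliance on missing at random: bias remains if dropout depends on the unseen score (about +0.11 SD in the assumed one-arm case), and no partial data are recovered if dropouts leave before any follow-up.

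### Section 3.3 names no primary outcome or time point and controls no error across at least 11 between-group tests, so the chance of a false positive is several times the nominal 5%

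*Combined protocol and SAP*

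**What the plan says.** Section 3.3 sets out the comparisons item by item.

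- Item 4 compares the belief total over time by repeated-measures analysis of variance.
- Item 5 compares the belief dimensions, the behaviour score and daily oxygen time by a generalized linear mixed model.
- Item 6 returns to all of these with a t-test or rank-sum test at the separate time points: "Comparison between groups of the total scores and scores of each dimension of long - term home oxygen therapy beliefs", then the behaviour score and daily oxygen time.
- Item 7 adds within-group tests of the same outcomes.
- Item 8 begins "Comparison of the differences in the scores of the Montreal Cognitive Assessment Scale, Mini - Mental State Examination" and goes on to a depression and an anxiety scale, all by t-test.

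Section 3.2 gives the number of belief dimensions: "The questionnaire consists of four dimensions and 26 items".

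The only significance level in the document is in the sample-size paragraph of section 3.1: "With a significance level of 0.05 and a Type II error probability of 0.1". It belongs to a comparison of two rates, where "the oxygen therapy compliance rate is 20%, and it is expected to increase by 40% after intervention". Section 3.3 states no level, primary outcome, primary time point, test order or adjustment, and it has no analysis of the compliance rate.

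**The concern.** The sample size was set for one comparison at 0.05, but the analysis section offers many comparisons and not that one. All the listed outcomes therefore have equal standing, and any one of them could be put forward as showing that the education works.

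Two features add to this. The belief questionnaire alone gives five tests per visit, its total and four dimensions, although the dimensions presumably make up the total. And the seven outcomes in item 6 are also tested in items 4 and 5 by other methods, with no statement of which result prevails or whether the model result must pass before visit-by-visit tests are read.

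At stake is the meaning of the 0.05: it would not describe the risk of a false claim from this trial.

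**Working it through.** **The plan's own figure.** Inputs from section 3.1: rates 20% and 60% (the increase read as 40 percentage points), alpha 0.05 (two-sided assumed), power 0.90. With p̄ = 0.4, n = 2·p̄(1 − p̄)·(1.960 + 1.282)² / 0.4² = 0.48 × 10.51 / 0.16 = 31.5, rounded up to the stated 32 per group. Adding 20% gives 32 × 1.2 = 38.4, rounded up to the stated 39. The sample size reproduces, and it is for a single test at 0.05.

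**Counting the tests.** Item 6 has 1 belief total + 4 dimensions + behaviour score + daily oxygen time = 7 per time point. Item 8 has 4 scales, assumed tested once each. The number of post-baseline visits V is not stated, so the count is 7V + 4: 11 for one visit, 18 for two, 25 for three. This leaves out items 4 and 5 (second tests of the same data), item 7 (within-group tests), and the activities-of-daily-living score and seven ventilation indicators that section 3.2 collects but section 3.3 gives no test.

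**Independent tests, no true effect.** Any false positive: 1 − 0.95^k. One favouring the education: 1 − 0.975^k.

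- k = 11: 1 − 0.95^11 = 0.431; 1 − 0.975^11 = 0.243
- k = 18: 1 − 0.95^18 = 0.603; 1 − 0.975^18 = 0.366
- k = 25: 1 − 0.95^25 = 0.723; 1 − 0.975^25 = 0.469

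**Correlated tests.** Independence overstates the risk, so null trials were simulated from multivariate normal outcomes with the belief total set as the sum of its dimensions. The moderate case has 31 per group (39 × 0.8 = 31.2), correlation 0.3–0.5 between outcomes and 0.6 between visits. The wider case has 0.3–0.8 between outcomes and 0.5–0.8 between visits. All correlations are assumptions. Each cell shows any false positive / one favouring the education.

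| Follow-up visits | Tests | Independent | Moderate correlation | Wider range |
|---|---|---|---|---|
| 1 | 11 | 43% / 24% | 33–36% / 17–18% | 24–38% / 12–20% |
| 2 | 18 | 60% / 37% | 44–49% / 21–25% | 30–51% / 16–28% |
| 3 | 25 | 72% / 47% | not tabulated | 34–60% / 18–34% |

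The moderate figures depend somewhat on how the item 8 scales relate to the other outcomes. A recheck with those scales either uncorrelated or correlated with the rest gave 29–38% / 15–20% for one visit and 44–50% / 22–28% for two. The nominal values are 5% / 2.5%. With one visit, 33–36% and 17–18% are each about seven times nominal.

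**The case against.** A reader might infer that a chance benefit is likely. The documents do not support that. The larger percentages count false positives in either direction, including results against the education. In the favourable direction the figure is 12–47% across one to three visits, from strongly correlated to independent tests, and so stays below one half.

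A reader might also take 14 or 18 tests as what the plan prescribes. It does not say how many visits there are; two is an assumption. Without assuming several visits, the text supports 7 tests, or 11 with item 8. Nor does section 3.3 say that each test is at 0.05. That is inferred from the sample-size paragraph, reasonably, since no other level is given.

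The strongest defence is that the sample-size paragraph in effect names compliance as the main outcome, and that strict adjustment of secondary outcomes is a matter of judgement in a 78-patient nursing education trial. The second half stands: with one primary test named, the main claim is protected without adjusting the rest. The first half does not rescue the plan as written. The compliance rate is never called primary and section 3.3 does not analyse it. Daily oxygen time and the behaviour score are related to it, but they are compared as scores or hours, not as a rate, and have no precedence over the other outcomes.

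**Conclusion.** The point holds. Followed as written, section 3.3 lets any one of at least 11 between-group comparisons count as success, with no primary outcome, no primary time point and no error control. With one follow-up visit and moderate correlation, the chance of at least one false positive is about 33–36%, and of one favouring the education about 17–18%. With two visits the figures are about 44–49% and 21–25%. These rest on three assumptions: two-sided 0.05 for each test, the number of visits, and the correlations. The excess over the nominal 5% and 2.5% holds in every scenario examined. The sample-size calculation is not affected. The change should be made before the data are analysed.

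**What to change.** Amend section 3.3 as follows.

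1. Name one primary test, at two-sided 0.05: the between-group comparison of the oxygen therapy compliance rate on which the sample size is based, at one stated follow-up. The sponsor must state what counts as compliant and list the visits.
2. Label all other outcomes secondary.
3. For the belief total, behaviour score and daily oxygen time, put the group-by-time test in items 4 and 5 first. Read the item 6 tests as significant only if that test passes.
4. Report the belief dimensions, intermediate visits and all four item 8 scales as group differences with 95% confidence intervals, without significance claims.
5. If confirmatory secondary claims are wanted, test the belief total, behaviour score and daily oxygen time with Holm's method only after the primary test succeeds. The overall error then stays at 0.05. Without that condition, a separate 0.05 for the secondary set could bring it to about 1 − 0.95 × 0.95 = 9.75%.

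The cost is wording only, with no new data and every planned analysis kept. Fewer results can be called significant. If Holm is used for three outcomes, its strictest step is 0.05 / 3 = 0.0167. As a guide from a two-sample t-test with 31 per group, power at that step falls from 87% to 75% for a difference of 0.8 SD, and from 97% to 93% for 1.0 SD.
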